15.5 LEVELS OF SIGNIFICANCE

Given that no hypotheses are to be tested in this study, no levels of significance are specified.

15.6 ANALYSIS SETS

There will be two primary analysis sets:

- The Full Analysis Set will be defined as all subjects in whom the microwave ablation procedure is completed and who provide information on ablation margins for evaluation

of Technical Success and Technique Efficacy. The Full Analysis Set will be the primary analysis population for summary of the primary endpoint and effectiveness-related secondary endpoints.

- The Safety Set will consist of all subjects in whom the microwave ablation procedure is attempted, i.e. started and regardless of whether it was completed as planned or not. The Safety Set will be the primary analysis population for all safety-related endpoints.

Additional analysis sets may be determined to be necessary (e.g. Per Protocol) pending trial progress and will be identified in the SAP as needed.

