15.7 SAMPLE SIZE JUSTIFICATION

A sample size of at least 30 subjects is planned for this study. This is a single arm study and as such, the sample size is not statistically powered for the evaluation of a specific hypothesis, but rather is deemed sufficient to provide meaningful information for evaluation of the specified endpoints and will allow for an informed comparison to existing literature on microwave ablation results. The study will continue to enroll subjects until at least 30 subjects have completed the 3-month visit.

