15.8 ANALYSES TO BE CONDUCTED

15.8.1 Disposition of Study Subjects

Subject disposition will be summarized using counts and percentages. The number and percentage of subjects consented, included in each analysis set, completed and discontinued will be tabulated along with the specific reasons for discontinuation.

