15.8.3 Primary and Secondary Endpoint Analyses

The number and percentage of subjects achieving Technical Success, defined as complete tumor ablation with adequate or insufficient ablation margin, based on contrast-enhanced MRI and CT scans immediately following the ablation procedure, will be summarized and an exact 95% confidence interval will be estimated. A similar summary will be provided for Primary Technique Efficacy, defined as complete tumor ablation with adequate or insufficient ablation margin, based on contrast-enhanced MRI and CT scans follow-up at 1 month after the ablation procedure.

Local tumor progression rates at 1, 3, 6, 9, 12, 18, 24, 30 and 36 months will be estimated using the Kaplan-Meier method and 95% confidence intervals will be provided. Only subjects providing an observation at the given time point will be included in the analysis. A similar summary will be provided for the 36-month for overall and progression free survival rates.

Summary statistics as appropriate for continuous or categorical measurements will be provided for all other secondary effectiveness parameters.

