15.8.5 Handling of Missing Data and Dropouts

All summaries will be performed only on subjects undergoing the ablation procedure and only observed data will be summarized. There will be no imputation of data for early terminated subjects or for enrolled subjects who do not provide a measurement at a given visit. Subjects who terminate prior to the 3-month visit will be replaced. Subjects terminating at or after the 3-month visit will not be replaced.

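### Ablations that are started and then abandoned drop out of both numerator and denominator of Technical Success, the only primary endpoint, and no analysis of all started ablations is planned

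*Combined protocol and SAP*

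**What the plan says.** Section 15.6 defines two primary analysis sets.

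- The Full Analysis Set is "all subjects in whom the microwave ablation procedure is completed and who provide information on ablation margins for evaluation" of Technical Success and Technique Efficacy. Its role is stated directly: "The Full Analysis Set will be the primary analysis population for summary of the primary endpoint and effectiveness-related secondary endpoints".
- The Safety Set is "all subjects in whom the microwave ablation procedure is attempted, i.e. started and regardless of whether it was completed as planned or not". It serves the safety endpoints.

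Section 15.8.3 then summarizes "The number and percentage of subjects achieving Technical Success, defined as complete tumor ablation with adequate or insufficient ablation margin", with an exact 95% confidence interval. It gives no separate denominator and no failure rule. Section 15.8.5 restricts summaries to observed data, rules out imputation, and adds: "Subjects who terminate prior to the 3-month visit will be replaced". Section 8.5 requires intra-treatment withdrawal only for a conversion that happens before ablation begins.

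Two provisions bear on transparency and later change. Under 15.8.1, "The number and percentage of subjects consented, included in each analysis set, completed and discontinued will be tabulated". Section 15.6 closes with: "Additional analysis sets may be determined to be necessary (e.g. Per Protocol) pending trial progress and will be identified in the SAP as needed".

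**The concern.** The two definitions in 15.6 show that the authors expected some procedures to start and not finish as planned. Those procedures are kept for safety, while completion is required for effectiveness. In a single-arm study the denominator is part of the result, and this one is conditioned on something that happens after treatment has begun and is likely to be linked to the outcome. An ablation broken off part-way is the kind of case most likely to leave viable tumor.

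Replacement can hide the effect further. A subject whose ablation is abandoned and who leaves before month 3 is replaced by a new subject, so the reported denominator can still be 30.

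At stake is the reading of the one primary endpoint. Section 15.7 justifies the sample on the ground that it "will allow for an informed comparison to existing literature on microwave ablation results". A rate that leaves out abandoned attempts describes finished procedures, not the procedure as undertaken.

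**Working it through.** **How each kind of case is treated.**

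1. *Procedure finished, residual tumor on the scan.* It is in the Full Analysis Set and classed as incomplete tumor ablation (9.1, 11.11), so it already counts as a failure.
2. *Procedure finished, no evaluable scan.* It gives no margin information, so it is outside the Full Analysis Set under the plan's observed-data principle.
3. *Procedure started and abandoned.* It is in the Safety Set. It fails the completion condition of 15.6 whether or not it was scanned. 15.8.3 has no rule that brings it back, 15.8.5 does not impute, and 8.5 deals only with conversions before ablation starts. It is therefore in neither numerator nor denominator.

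The gap is case 3 alone.

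**Inputs.** The planned size is at least 30 subjects completing month 3 (15.7). It has no stated derivation, so there is no planned figure to reproduce. The number of abandoned ablations is not given and is assumed below. Every completed procedure is assumed to have an evaluable scan.

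**Formulas.** Let s be the successes among n subjects in the Full Analysis Set, and k the abandoned ablations counted as failures.

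- Plan: s/n. All started: s/(n + k).
- Difference: s/n − s/(n + k) = s·k / [n(n + k)].
- Exact (Clopper–Pearson) 95% limits for x out of n: lower = 2.5% quantile of Beta(x, n − x + 1); upper = 97.5% quantile of Beta(x + 1, n − x).

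Example with s = 29, n = 30: for k = 1 the difference is 29/(30 × 31) = 0.031; for k = 2 it is 58/(30 × 32) = 0.060.

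| Assumed case | Plan reports | All started | Plan minus all started (points) |
|---|---|---|---|
| One abandoned failure, leaves before month 3, replaced | 29/30 = 96.7% (82.8–99.9) | 29/31 = 93.5% (78.6–99.2) | 3.1 |
| Same, no other failure | 30/30 = 100% (88.4–100) | 30/31 = 96.8% (83.3–99.9) | 3.2 |
| Same, two other failures | 28/30 = 93.3% (77.9–99.2) | 28/31 = 90.3% (74.2–98.0) | 3.0 |
| One abandoned failure, stays to month 3 and counts toward the 30 | 28/29 = 96.6% (82.2–99.9) | 28/30 = 93.3% (77.9–99.2) | 3.2 |
| Two abandoned failures, both replaced | 29/30 = 96.7% (82.8–99.9) | 29/32 = 90.6% (75.0–98.0) | 6.0 |
| One abandoned, but the scan shows complete ablation | 28/30 = 93.3% | 29/31 = 93.5% | −0.2 |
| None abandoned | s/n | s/n | 0 |

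**How likely is at least one case?** For an assumed abandonment rate q, the chance of one or more in 30 is 1 − (1 − q)^30. That gives 26% at q = 1%, 45.5% at 2% and 78.5% at 5%. None of these rates comes from the documents.

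**The case against.** The strongest reply has four parts.

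- *The plan is not silent.* A reader might infer that the handling of abandoned ablations is simply unspecified. The documents do not support that: 15.6 and 15.8.5 together imply that these subjects drop out. What stands is that the exclusion is not justified and has no accompanying analysis.
- *The main type of failure is already counted.* Residual tumor after a finished procedure is a failure within the set. This is correct and confines the problem to abandoned ablations, which may never occur.
- *There are safeguards.* 15.8.1 will show the size of each set, and 15.1 and 15.6 allow a later SAP to add sets. But the set sizes do not give the success rate among all started ablations, and a shortfall from the Safety Set would mix abandoned with unscanned cases. The only added set named is Per Protocol. The SAP is due only before database lock, whereas the primary outcome is imaged within 4 days of each procedure, so a denominator settled late could be chosen with results in view.
- *The shift is small.* Three points is well inside the 17.1-point interval for 29/30 (99.9 − 82.8). This is fair. The shift nevertheless has a likely direction.

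Two further readings go too far. A reader might take completion in 15.6 to mean complete ablation on imaging, since 9.1 says the scans confirm completion; the primary endpoint would then be circular. That reading would leave the incomplete-ablation category empty, and the Safety Set wording uses completion in a procedural sense.

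A reader might also set the 3 points against the spread of microwave results in Tables 3 and 4. Those series mix HCC with metastases, access routes and denominators: the 99.3% for 53 patients with 149 tumors fits 148/149 = 99.3%, not 52/53 = 98.1%. Nor do the documents say whether the cited studies counted abandoned procedures. The spread is therefore no yardstick.

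**Conclusion.** The point holds and should be fixed. As written, 15.6 with 15.8.5 removes started-but-abandoned ablations from the only primary endpoint, and no analysis of all started ablations is planned. With about 30 subjects, each abandoned failure raises the reported rate by about 3 points, and two raise it by about 6.

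This rests on an assumed number of abandoned ablations and on their being failures. The effect is zero if none is abandoned, and nil or slightly reversed if an abandoned case proves complete on imaging. It is a risk in the rule, not evidence that any result is inflated. The study tests no hypothesis and sets no significance level (15.4, 15.5), and the first analysis is not used for early stopping (15.8.4), so no formal decision changes.

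**What to change.** - **15.6 and 15.8.3.** Define the Technical Success population as all subjects in whom ablation was started, except those whose procedure was completed but who have no evaluable post-procedure scan. Classify every scanned subject by the existing imaging definition, whether or not the procedure was completed. Count a started-but-not-completed procedure without a scan showing complete tumor ablation as not successful.
- **15.8.5.** Add an explicit exception to the observed-data and no-imputation rule for that case only. Without it, the two sections would conflict.
- **Sensitivity analysis.** Repeat Technical Success on the full Safety Set, also counting completed-but-unscanned subjects as failures.
- **Unchanged.** Keep the Full Analysis Set for the other effectiveness endpoints and the baseline table (15.8.2), and state that Technical Success uses a different population.

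The cost is wording in three sections, one extra table and possibly one eCRF field, because 11.3 lists no explicit item for completion status even though the current Full Analysis Set already depends on it. The reported rate may be slightly lower. If no ablation is abandoned, the primary result is the same as under the present text.

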7.2 STUDY ENDPOINTS

Primary:

Technical Success, defined as complete tumor ablation with adequate or insufficient margin, based on contrast-enhanced MRI and CT scans immediately following the ablation procedure.

Secondary:

- Primary Technique Efficacy, defined as complete tumor ablation with adequate or insufficient ablation margin, based on contrast-enhanced MRI and CT scans follow-up at 1 month after the ablation procedure;
- Local tumor progression (LTP) rate, evaluated at 1, 3, 6, 9, 12, 18, 24, 30 and 36 months after the ablation of the index tumor;
- Primary efficacy rate, defined as the percentage of target tumors successfully eradicated following the ablation procedure;
- Secondary efficacy rate, defined as the percentage of tumors that have undergone successful repeat ablation following identification of local tumor progression;
- Progression free survival and overall survival rates at 36 months after the ablation procedure;
- Rate of adverse events reported through 3 months and cumulatively through study completion; Quality of Life, as measured by VAS pain score, EORTC QLQ-C30 and EORTC QLQ-HCC18, before the ablation procedure and at each post-ablation visit;
- Health economics associated with the ablation procedure: complete procedure time, ablation time, no. of ablations, length of stay, no. and types of probes used.

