9.0 STUDY PROCEDURES

9.1 PROCEDURE DESCRIPTION

A multi-disciplinary team at the site will determine with the help of imaging, whether a patient is suitable for local ablation therapy, and the type of ablation procedure that is required, based on the stage, location and cell types associated with the liver tumor. Potential candidates for microwave ablation will undergo liver, renal function, coagulation, Alpha-fetoprotein (AFP) and CBC tests before the procedure to ensure that they will have adequate liver capacity following the ablation.

[figure not shown]
Microwave Ablation Procedure

All ablations will be performed under general anesthesia with deep sedation via percutaneous approach by trained interventional radiologists who are experienced with tumor ablation. Microwave ablation is a minimally invasive procedure that uses electromagnetic waves to generate tissue necrosis in the liver in this study. Using contrast-enhanced ultrasound imaging guidance, a small probe is inserted percutaneously into the lesion.

The ablation will be performed with a single high-powered, gas-cooled, multiple antenna-capable microwave system (NeuWave Medical's Certus 140™ 2.45 GHz Ablation System) with single or multi-probe antennas, according to the IFU and the performing physician's clinical judgment. Electromagnetic waves are delivered to the tissue, producing frictional heating to generate tissue necrosis at $> 60^{\circ}\text{C}$. Duration of treatment and power application will be determined by the performing physician based on manufacturer guidelines, with adjustment for tumor size, proximity to vulnerable structures, and real-time intraprocedural monitoring. Antenna placement will be performed under real-time contrast-enhanced ultrasound imaging guidance. Single or multiple ablation sessions may be done in one procedure. It is suggested that the physician considers using more than one probe for lesions ≥ 2 cm.

At the end of the ablation, contrast-enhanced MRI and CT scans will be done to confirm the completion of the ablation procedure (up to 4 days after the date of the ablation procedure). According to the standard practice at the site in Korea, ablation confirmation will be classified as:

- complete tumor ablation with adequate margin
- complete tumor ablation with insufficient margin
- incomplete tumor ablation.

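### Read as written, Section 15.6 makes 1-month margin data a condition for entering the primary-endpoint population, so observed Technical Success results, and probably early deaths, can drop out

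*Combined protocol and SAP*

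**What the plan says.** Section 15.6 defines the Full Analysis Set as subjects in whom ablation is "completed and who provide information on ablation margins for evaluation", and the sentence goes on "of Technical Success and Technique Efficacy". It makes this set the "primary analysis population for summary of the primary endpoint and effectiveness-related secondary endpoints". The Safety Set, which is everyone in whom ablation was started, is assigned to safety endpoints only.

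The two margin assessments fall at different times. Section 9.1 places the post-ablation scans "up to 4 days after the date of the ablation procedure". Section 7.2 bases Primary Technique Efficacy on MRI and "CT scans follow-up at 1 month after the ablation procedure", with a window of ±14 days in Section 15.3.

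Section 7.2 also lists "Progression free survival and overall survival rates at 36 months after the ablation procedure" among the secondary endpoints. No section says which analysis set they use.

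On early exits, Section 15.8.5 says: "Subjects who terminate prior to the 3-month visit will be replaced". It summarises observed data only, without imputation. Section 15.8.3 limits the Kaplan-Meier estimates of local tumor progression to subjects observed at the time point, and says that overall and progression-free survival will be summarised similarly.

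**The concern.** Technical Success is fully known within days of the procedure. A membership rule that also asks for a 1-month read makes the primary-endpoint population depend on what happens afterwards. A subject read as incompletely ablated who leaves before the 1-month scan is an observed failure, yet is not counted.

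Survival has a related problem. Follow-up runs from ablation, so if the set is used for survival, everyone in it has by definition lived to the 1-month scan, and a death before it is an observed event that disappears.

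The study has no control arm, and Section 15.7 intends its results to be compared with published microwave series. A selected denominator would carry straight into that comparison. With about 30 subjects, each one is worth about 3 percentage points.

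**Working it through.** **Who is affected.** Take subjects with a completed ablation and a post-ablation read.

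- *Death before the 1-month scan:* no 1-month margin data, so outside the set on the plain reading.
- *Voluntary withdrawal before the scan:* outside the set. Technical Success is observed, but survival is only censored.
- *Chemotherapy or radiation for HCC within 30 days:* Section 8.5 lists this as a reason for mandatory withdrawal. If it precedes the scan, the subject is outside the set.
- *Surgery or repeat ablation:* not a listed reason for post-treatment withdrawal. Section 11.10 moves subjects re-treated after progression or recurrence to reduced follow-up and does not terminate them.
- *Any switch of treatment in a subject who still has the 1-month scans:* stays in.

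Sections 8.5 and 15.8.5 then replace those who terminate before the 3-month visit.

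**Does another section readmit them?** Section 15.8.5 governs missing measurements, not set membership. Section 15.8.3 gives no separate denominator for Technical Success. Section 15.8.1 counts each analysis set and gives reasons for discontinuation, which shows the loss but does not restore the outcome.

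**Size.** The plan gives no precision or power calculation for its 30 subjects, so there is no figure of its own to reproduce. It also gives no early-loss rate, so 1 to 3 losses in addition to 30 retained subjects are assumed.

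Exact (Clopper-Pearson) 95% limits for x of n: lower = Beta(0.025; x, n−x+1), upper = Beta(0.975; x+1, n−x). When x = n the upper limit is 1.

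If all 30 retained subjects are successes and the lost ones are failures:

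| Failures lost | Under the rule | All restored |
|---|---|---|
| 1 | 30/30 = 100% (88.4 to 100) | 30/31 = 96.8% (83.3 to 99.9) |
| 2 | 30/30 = 100% (88.4 to 100) | 30/32 = 93.8% (79.2 to 99.2) |

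Starting from 28/30 = 93.3% (77.9 to 99.2):

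- Lost subjects all failures: 28/31 = 90.3%, 28/32 = 87.5%, 28/33 = 84.8%. The rule overstates by 3.0, 5.8 and 8.5 points.
- Lost subjects all successes: 29/31 = 93.5%, 30/32 = 93.8%, 31/33 = 93.9%. The rule understates, by under 1 point each time.

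Overall survival at 36 months, as simple proportions (equal to Kaplan-Meier if no one is censored earlier): 21/30 = 70.0% with early deaths omitted. Restoring 1, 2 or 3 gives 21/31 = 67.7%, 21/32 = 65.6% and 21/33 = 63.6%.

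The chance of at least one loss before the 1-month scan among 30 treated is 1 − (1 − r)^30. For assumed r of 1%, 3%, 5% and 10% this is 26%, 60%, 79% and 96%.

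**The case against.** - **The sentence can be read otherwise.** It could mean margin data for whichever of the two endpoints is being summarised. The observed-data approach of Section 15.8.5 fits that reading, and the observation rule in Section 15.8.3 would be largely redundant at month 1 if everyone already had a 1-month read. This stands as a doubt about intent. It does not remove the need to reword, because two statisticians could build different primary populations from the same sentence.
- **Survival on this set is inferred.** A reader might take it as stated that progression-free and overall survival use the Full Analysis Set. Section 15.6 says only effectiveness-related secondary endpoints, and no section labels these two as such. The inference is natural, since Section 15.8.3 analyses them beside the effectiveness endpoints and no other population is named, but it remains an inference.
- **Not every switch of treatment excludes.** A reader might infer that any early change of therapy, including surgery, removes and replaces the subject. Section 8.5 does not support that.
- **Not every exclusion flatters the result.** The direction depends on who is lost, as the figures above show.
- **The illustration is a worst case.** Section 4.2 cites a series of 3 to 5 cm HCC with 93% technical effectiveness and one procedure-related death. Table 4 lists that series as 182; at 1/182, the chance of at least one such death among 30 is 1 − (181/182)^30, about 15%, and its timing is not given. The two HCC series with this device report 100% technical success. The survival shift of 2.3 points is small beside an exact interval of 50.6% to 85.3% for 21/30.
- **The stakes are limited.** Sections 15.4 and 15.5 specify no hypothesis or significance level, the exclusions will be tabulated, and deaths are reportable throughout. This bears on how serious the point is, not on whether it is right.

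**Conclusion.** The point holds for the plain reading of Section 15.6. Requiring a 1-month read for entry can remove an observed primary outcome, and no other section restores it. For survival it holds on the further assumption that the Full Analysis Set is the intended population.

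The effect is favourable when failures or early deaths are lost: about 3 points of Technical Success per lost failure, and 2.3 points of 36-month survival for one omitted death when the reported figure is 70.0%. These are illustrations under assumed losses, not predictions. The documents do not support saying that such subjects will certainly be deleted, or that every exclusion improves the result.

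This should be fixed, and ideally before the first analysis, since that analysis reports Technical Success. It is not critical, because the study is descriptive and Section 15.8.1 will show how many subjects each set excludes.

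**What to change.** 1. In Section 15.6, remove the 1-month Technique Efficacy condition from Full Analysis Set membership.
2. Analyse Technical Success in every subject with a completed ablation and a post-ablation read, whatever happens later.
3. Analyse Primary Technique Efficacy in subjects with a 1-month read, and show beside it the number missing and the reasons.
4. Name the population for progression-free and overall survival as all treated subjects, followed from the day of ablation, with early deaths as events and withdrawals censored.
5. In Section 15.8.3, state that the restriction to subjects observed at the time point does not apply to these Kaplan-Meier analyses. Left in place, it could itself remove early deaths whatever set is used.
6. State in Section 15.8.5 that replaced subjects stay in the analyses.

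The cost is protocol and SAP wording only, with no new visits or data. Reported rates may come out slightly less favourable.
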